Primary Endpoints: 1. Lower Extremity Perfusion: Measurement of lower extremity perfusion at 4 weeks of continuous device usage. Peripheral perfusion will be measured at baseline, 48 hours, 1 week and 4 weeks. Ankle Brachial Index (ABI) and Skin Perfusion Pressure (SPP) will be used to evaluate perfusion status for all study participants.

2. Plantar Pressure: Measurement of plantar pressure compared to the standard (non-PulseFlow DF) offloading boot.

Secondary Endpoints:

The following secondary effectiveness endpoints will be evaluated but success will not be required for determining success of the study. 1) Balance: Improvement in balance and decrease in fall risk as measured using a validated body worn sensor system at baseline and 4 weeks. 2) Activity Measurement: Activity measurement during 48 hours of continuous daily physical activity using a validated body worn sensor system, measured at baseline and 4 weeks. 3) Gait assessment using validated wearable technology at baseline and 4 weeks.

Primary Safety Endpoints: 1) The occurrence of adverse events during the four (4) weeks of the study treatment that are possibly related, probably related, or definitely related to PulseFlow DF (e.g. deterioration in wound condition such significant increase in wound size, infection, etc, falls, serious adverse events) will be properly reported.

Other assessments: 1) Usability assessment 2) Patient perception of benefit and level of comfort (Scoring System); 3) Adherence to use of offloading boot; and 4) Others: Quality of life, fear of falling, frailty, etc.

The key goals of the proposed project are to test whether a specially designed compression device can improve lower extremity perfusion, whilst also simultaneously improving the balance and walking performance. We envision the use of this specially designed offloading device with compression capability will help reduce the incidence of diabetic foot ulcers in high-risk diabetic patients. In addition, we assumed the proposed device might enhance daily physical activity as well as walking performance. We will conduct a prospective clinical study to validate these hypotheses. Potential changes in walking and spontaneous daily physical activities will be assessed using validated technologies that include walking analyzer system, balance assessment using body worn sensors, and computerized pressure insoles.

Section E: Protocol Risks/Subjects

E1. Risk Category

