Category 2: Research involving greater than minimal risk, but presenting the prospect of direct benefit to the individual subjects.

E2. Subjects

Gender:

Both

Age:

Adult (18-64 yrs), Geriatric (65+ yrs)

Ethnicity:

All Ethnicities

Primary Language:

English, Spanish

Groups to be recruited will include:

Patients

Which if any of the following vulnerable populations will be recruited as subjects?

Vulnerable populations require special protections. How will you obtain informed consent, protect subject confidentiality, and prevent undue coercion?

E3. Pregnant woman/fetus

Will pregnant women and/or fetuses (as described in 45 CFR 46 Subpart B) be enrolled in the research?

No

E4. Neonates

Will neonates of uncertain viability or nonviable neonates (as described in 45 CFR 46 Subpart B) be enrolled in the research?

No

E5. Children

Will children be enrolled in the research?

No

Section F: Design/Procedure

F1. Design

Select one category that most adequately describes your research:

c) Pilot

Discuss the research design including but not limited to such issues as: probability of group assignment, potential for subject to be randomized to placebo group, use of control subjects, etc.

In this proof of concept, intent to treat trial, 15 consecutive patients with diabetes and risk for lower extremity ulcers will be recruited from all study sites. Patients will be consented per the local Institutional Review Board's guidelines and approval for this study.

Inclusion Criteria:

a) Males or females age 18-80 years old with history of type 1 or 2 diabetes and the ability and willingness to provide Informed consent b) Patients with diabetic foot ulcers c) Patient is willing to participate in all procedures and follow up evaluations necessary to complete the study. d) Patients who have undergone lower extremity surgery / amputation may be enrolled into the study to the clinical judgment of the Investigator

Exclusion Criteria:

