Assessment of user friendliness, acceptability, and perception of need: We will use a questionnaire tailored to the topic of this study to evaluate the perception of the target population in receiving benefit from the proposed technology. Subjects are asked to answer the questionnaire at the end of study. The questionnaire includes 11 items and allows assessing how target population perceives the need of such technology in management of their problem.

Other assessments: Other relevant assessments are Demographic/Health questionnaire, the Montreal Cognitive Assessment, the mobility-tiredness scale, Barthel Index, Depression Scale, fear of falling (Short-Falls Efficacy Scale – International), quality of life (Promise Global General Health Questionnaire), digital photography, Fried Frailty Criteria, Foot Questionnaire, Pain Assessment, Fall Log and Contact Agreement, Physical activity log, follow-up questionnaire, Shoe-fit test , subject’s perception assessment compared to standard shoe and RCW assessed using a 10 point Likert scale questionnaire.

PulseFlow DF: The PulseFlow device will be given to the subject. The research personnel will make sure that the subject is comfortable with the device and the device itself provides the offloading that is needed. The research personnel will also provide device education to the participants and will answer any questions that may arise.

Study Day 1, Visit 2 48-hour follow: All participants will be asked to return to clinic approximately 48 hours after visit 1. In this visit, (1) any adverse events will be assessed; (2) activity measurement (body sensor) will be returned; (3) PulseFlow DF data will be downloaded to ensure operability and patient compliance; and (4) further device education will be provided in case any issues have risen. We will take digital photographs of the participants feet and collect edema information.

Study Day 2, Visit 3 1-week follow-up: All participants will be asked to return to clinic approximately 1 week after visit 1. In this visit, (1) any adverse events will be assessed; and (2) PulseFlow DF data will be downloaded to ensure operability and patient compliance. Device education will be provided if needed. The participant will be asked to return the device at their next visit. We will take digital photographs of the participants feet and collect edema information.

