Study Day 3, Visit 4 4-week follow-up: All participants will be asked to return to clinic approximately 4 weeks after visit 1. In this visit, outcome assessment using similar assessments described for Study Day 0 will be performed. In addition, perception of benefit and user-friendliness of the PulseFlow DF® will be assessed using a questionnaire. We will take digital photographs.

Participants will be asked to wear a comfortable shirt which holds a small activity monitor (PAMSys) for a period of 48 Hours (2 days). Patients will be requested to return this device via a pre-paid FEDEX envelope

Study Day 4, Visit 5 Follow-up up to three months: Some participants may be contacted by the study coordinator approximately up to three months post the last study visit to document success of wound healing if they continue to use PulseFlow DF after 4 weeks as well as potential incident of re-ulceration, or incident of falls.

We will ask participants to provide an Emergency Contact.

We will ask participants if they would like to be contacted for further studies they may be eligible for.

****Please note that the protocol attached to Section S is from the University of Arizona. The PI initially established this protocol at U of A as it is an investigator initiated study. We have ensured that we have not included any references to U of A in this BCM protocol*****

Section G: Sample Size/Data Analysis

G1. Sample Size

How many subjects (or specimens, or charts) will be used in this study?

Local: 50 Worldwide: 50

Please indicate why you chose the sample size proposed:

We intend to employ a simple minimal risk research protocol to capture data required to realize the goals of this study. The results from this study will help us understand the real clinical needs and optimize the device specifications and form factor to fulfill these needs.

This is an initial proof of concept pilot study. The results of this study will allow for the calculation of an appropriate sample size for a larger proof of superiority (over current standard of care) trial.

G2. Data Analysis

Provide a description of your plan for data analysis. State the types of comparisons you plan (e.g. comparison of means, comparison of proportions, regressions, analysis of variance). Which is the PRIMARY comparison/analysis? How will the analyses proposed relate to the primary purposes of your study?

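### The primary safety endpoint leaves out adverse events judged unrelated to the device, in a study with no safety control against which to check that judgement

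*Combined protocol and SAP*

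**What the plan says.** Section D (Primary Safety Endpoints) gives a single safety endpoint, restricted to events "that are possibly related, probably related, or definitely related to PulseFlow DF". The time window is the four weeks of treatment. The events it lists, "deterioration in wound condition such significant increase in wound size, infection, etc, falls, serious adverse events", are examples inside that restriction. They are not separate endpoints.

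Section F1 describes one group: "In this proof of concept, intent to treat trial, 15 consecutive patients with diabetes and risk for lower extremity ulcers will be recruited". Section F2 gives the device to each subject. The removable cast walker or standard boot appears only in within-subject gait and plantar pressure tests.

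In Section F2, the 48-hour visit (Visit 2) and the 1-week visit (Visit 3) each state that "any adverse events will be assessed", with no restriction by relatedness. The 4-week visit (Visit 4) says only that "outcome assessment using similar assessments described for Study Day 0 will be performed". The Day 0 list contains a fall log and wound measurement but no adverse event assessment.

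Section G2 sets out three hypotheses (offloading, circulation, activity and quality of life) and no safety analysis. Section H2 requires a Data and Safety Monitoring Plan as an attachment, which is not among the supplied documents.

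**The concern.** A relatedness filter is easiest to defend when a control arm lets the reader see how often the same events occur without the device. Here there is none for safety. Anyone judging causality in this study also knows that the patient was given the device.

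The events that matter most are the hardest to attribute. The background text says some ulcers persist and become infected, and that clinicians hesitate to use compression in patients with peripheral arterial disease. Section F1 excludes only severe disease (ABI below 0.5), so patients with milder disease can enrol. Section H1 lists insufficient offloading as a risk, and wound worsening from that cause would be hard to tell from natural progression. Any of these events could reasonably be put down to the patient's disease, and it would then leave the endpoint, even if serious.

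At stake is the usefulness of the safety result. Section G1 says the study should inform a larger superiority trial against standard of care. In planning safety for such a trial, a rate that does not depend on attribution is the more useful input.

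**Working it through.** The plan states no safety rate, threshold or safety sample-size calculation, so there is no figure to reproduce. The check is a comparison of the text, followed by an illustration.

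**Text comparison**

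| Element | Where | Content |
|---|---|---|
| Events counted | Section D | Only those judged possibly, probably or definitely related |
| Time window | Section D | Four weeks of treatment |
| Collection at 48 hours and 1 week | Section F2, Visits 2 and 3 | Any adverse event |
| Collection at 4 weeks | Section F2, Visit 4 | Not named; refers back to Day 0 |
| Concurrent safety control | Sections F1, F2 | None |
| Safety analysis | Section G2 | None |

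Two things follow.

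1. Events are collected without a filter at two visits but counted with one. Patients with a related event are a subset of patients with any event, so the endpoint rate is at most the all-event rate. The gap is set by attribution.
2. The last visit that names adverse event assessment is at about 1 week. The remaining 4 − 1 = 3 weeks of the window have no explicitly named collection point.

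**Illustration (all inputs assumed)**

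Suppose 4 of 15 patients have infection or wound worsening: 4/15 = 27%. If half are judged unrelated, the endpoint counts 2/15 = 13%.

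For a range, let p be the true four-week risk per patient and s the share of affected patients whose event is judged related. The expected number counted is n × p × s. The chance that at least one patient is counted is 1 − (1 − p × s)^n. For example, with n = 15, p = 0.20 and s = 0.5, the expected number is 1.5 and the chance is 1 − 0.90^15 = 0.794.

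Each cell shows expected patients counted, then the chance of at least one, for n = 15:

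| p | s = 100% | s = 50% | s = 25% |
|---|---|---|---|
| 10% | 1.5; 0.794 | 0.75; 0.537 | 0.375; 0.316 |
| 20% | 3.0; 0.965 | 1.5; 0.794 | 0.75; 0.537 |
| 30% | 4.5; 0.995 | 2.25; 0.913 | 1.125; 0.689 |

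Section G1 gives 50 subjects where Sections D and F1 give 15. With n = 50 and p = 20%, the expected counts are 10, 5 and 2.5, and the chances 1.000, 0.995 and 0.923. The proportional loss (the factor s) is the same at either size.

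**The case against.** The strongest defence is that the filter is broad. Its lowest category is possibly related, and the endpoint names wound deterioration, infection, falls and serious events as examples of what may count. Reporting device-related events is also a recognisable choice for a proof-of-concept device study with no safety hypothesis. Some key events can be described without any attribution: wound size is measured at baseline and again at 4 weeks, photographs are taken at follow-up visits, and there is a fall log. This stands as mitigation. It does not put an event judged unrelated back into the endpoint, and infection is less clearly covered by those other measurements.

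A reader might infer several stronger points that the documents do not support.

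- **That the endpoint can only understate harm.** It cannot exceed the all-event rate, but all events are not the same as device harm. With so inclusive a lowest category, background infections or falls could be attributed to the boot, so the filtered rate could also overstate harm caused by the device. The direction of error is not fixed.
- **That unrelated events will go unrecorded.** Section D does not say so, Visits 2 and 3 assess any event, and the unsupplied monitoring plan may require full recording.
- **That site staff judge relatedness.** The supplied text does not say who judges it. What follows from the design is only that the judgement cannot be blind to device use.
- **That a wide upper limit after zero counted events shows the fault.** Such a limit reflects sample size and would be the same for an unfiltered endpoint with zero events.

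All-event reporting would not establish causation in a single-group study either. Its merit is that the reported rate no longer depends on a judgement that cannot be checked.

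**Conclusion.** The point holds as one about the endpoint definition. As written, the only safety endpoint excludes events judged unrelated, the design offers no comparison by which to check that judgement, and Section G2 has no safety analysis to fill the gap.

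The size cannot be derived from the documents. The fall from 27% to 13% is an assumed example; in general the reported rate is the all-event rate multiplied by the share attributed to the device. The conclusion does not depend on whether 15 or 50 subjects are enrolled, or on the direction of attribution error. It would remain if the monitoring plan requires every event to be recorded, unless that plan also redefines the endpoint. For a pilot this is a change that should be made, but it does not invalidate the study.

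**What to change.** 1. In Section D, define the primary safety endpoint as all adverse events during the four weeks of treatment, regardless of relatedness.
2. In Section G2, add the analysis: number and percentage of patients with at least one event, with an exact 95% confidence interval. Show device-related events, serious events, falls, infection and wound deterioration as subsets.
3. In Section F2, Visit 4, add the statement already used at Visits 2 and 3 that "any adverse events will be assessed", covering the time since the 1-week visit.
4. Check that the Data and Safety Monitoring Plan agrees with these definitions.

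The cost is low: one more item at a visit that already takes place, and a reported rate that may look higher. No information is lost, because device-related events remain visible as a subset.

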a) Patients with severe peripheral vascular disease (ABI or ankle brachial systolic pressure index <0.5) b) Patients with diabetic foot ulcers in the plantar surface of the medial longitudinal arch of the foot c) Patients with active wound infection, or untreated osteomyelitis d) Patients currently on immunosuppressive drugs. e) Pregnant or breastfeeding females. f) Acute fractures of the foot g) Acute heart failure h) Participation in an interventional Study within the last 30 days i) Non-ambulatory or unable to stand without help or walk a distance of at least 6 feet without assistance. k) Patients with major foot amputation. j) Patients who are unable or unwilling to participate in all procedures and follow up evaluations h) Patients who do not fit to available PulseFlow® sizes (UK 5-11, US 7-10.5) provided by the Diabetic Boot Company

F2. Procedure

Following is a summary of study procedures:

Study Day 0 (initiation), Visit 1 The following baseline values will be assessed and recorded. In needed assessments, the podiatric physician will examine the patient providing standard of care treatment.

Screening/ Baseline: Subjects will be screened to ensure that they meet the inclusion and exclusion criteria. The study will be explained and written informed consent obtained from each patient prior to the initiation of screening procedures.

Cognitive assessment: The Montreal Cognitive Assessment (MOCA) is a series of questions used to assess cognitive status.

Physical exam: Physical exam will be conducted, including vascular, dermatological, and neurological, as part of a regular care visit.

Medical History: A detailed medical history will include: previous medical history, location and duration of previous ulcers, amputation (toe, foot, below knee, above knee), lower extremity bypass, lower extremity angioplasty, CABG, cardiac angioplasty, last visit by physician (in weeks), and current/past use of special shoes or insoles.

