Physical Performance Tests - Gait assessment: Gait performance will be assessed using by a validated body worn sensors (LegSys™, Biosensics LLC, USA). The device uses five sensor modules respectively attached to right and left anterior shins, right and left anterior thighs, and posteriorly to the lower back. Based on the subject’s height and using a two-link inverse pendulum model the following spatio-temporal gait parameters will be estimated: velocity, stride length, stride time, double support, single support, stride-to-stride variability, and gait initiation [20]. In addition, the COM range of motion during walking will be calculated by using the data from the sensor attached to lower-back. Gait will be assessed over a distance of 20 meters while wearing PulseFlow DF® under 2 conditions: (1) walking at habitual speed (2) walking at maximum speed (fast walking). In addition, the above tests will be repeated while wearing removable cast walker (RCW), which is a standard offloading device.

Plantar Pressure Assessment: The efficacy of PulseFlow DF® to reduce plantar pressure will be examined using computerized pressure insoles® (Fscan®, TekScan, Boston, MA). Subjects will be ask to walk a distance of approximately 20 feet at habitual speed while wearing a standard offloading boot and then while wearing PulseFlow DF®. In addition, to ensure that PulseFlow DF® is providing a comparable offloading to a standard offloading device, plantar pressure during standing (approximately 30 seconds) will be assessed while wearing a standard offloading device (e.g. Aircast Walker) and results will be compared while wearing PulseFlow DF®.

Objective assessment of physical activity: Spontaneous daily physical activities as well as the risk of falling during activity of daily living are quantified using a validated body worn sensor named PAMSys™ (Biosensics, LLC, USA). PAMSys is a small long-term recording movement sensor which is unobtrusively inserted into a comfortable shirt (PAMshirt™). The system contains inertial sensors with software developed to identify postural positions and movements such as walking, standing, sitting, or lying during a measuring period of 48 hr. It has proven to be sensitive (87–99%) and specific (87–99.7%)[21, 22] for postural position and detection of walking in different samples of older adults and patient groups.

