This study includes three hypotheses. To examine whether the proposed PulseFlow DF will provide comparable offloading as compared to removable cast walkers measured through a repeated measures study design for in shoe pressures (H1), we will use ANOVA and Fisher's exact tests for intra-subject reduction of peak pressures, pressure time integrals and Dynamic Plantar Loading Index.

To examine whether the proposed PulseFlow DF will help improve macro and micro-circulation in the lower extremity of patients (H2), we will use the similar analytical plan explained above by considering change in Skin perfusion pressure and ABI as dependent variables. For identifying the predictors, we will use multiple linear regression model and Anova (n-way). The independent variables will be severity of neuropathy quantified using Semmes Weinstein Monofilament, the level of activity, BMI, and age.

To examine whether the proposed PulseFlow DF will improve the activity level and quality of life (H3), we will use ANOVA multivariate test. The dependent variables will be number of total steps per day, duration of walking and standing, duration of longest episode of walking (i.e. continuous walking without stop), number of walking episode, duration of sit-to-stand and stand-to-sit postural transition, and SF12. We will use multiple linear regression model and multi-variant test to examine the effect of confounding parameters such as weather condition, BMI, age, etc.

Section H: Potential Risks/Discomforts

H1. Potential Risks/Discomforts

Describe and assess any potential risks/discomforts; (physical, psychological, social, legal, or other) and assess the likelihood and seriousness of such risks:

Some of potential risks could be discomfort, insufficient offloading, and uncomfortable level of compression to your plantar arch. It is important to notify us if you feel discomfort on wearing PulseFlow DF or if you feel excessive pressure to your feet because of wearing the PulseFlow DF.

You should always inspect the wound at each dressing change and comply with instructions providing by your doctor or wound care provider. You should immediately notify us or contact clinic, your doctor, or care provider if you feel the condition of your wound has been deteriorated. The signs of wound deterioration will be discussed with you by your doctor or care provider who treats your wound.

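### As written, the walking plantar-pressure test always runs standard boot first and PulseFlow DF second, so any effect of test order cannot be separated from the device difference

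*Combined protocol and SAP*

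**What the plan says.** Section D lists plantar pressure as the second primary endpoint: "Measurement of plantar pressure compared to the standard (non-PulseFlow DF) offloading boot". Section F2, under Plantar Pressure Assessment, describes two tests.

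- **Walking.** Subjects "walk a distance of approximately 20 feet at habitual speed", and they do so "while wearing a standard offloading boot and then while wearing PulseFlow DF".
- **Standing.** Pressure is recorded for about 30 seconds in each device. No order is stated.

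At Visit 4, "outcome assessment using similar assessments described for Study Day 0 will be performed"; no reversal of order is mentioned. Section G2 says that H1 concerns "comparable offloading as compared to removable cast walkers measured through a repeated measures study design for in shoe pressures (H1"), and that "we will use ANOVA and Fisher's exact tests for intra-subject reduction of peak pressures, pressure time integrals and Dynamic Plantar Loading Index". It names no term for test order or period.

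Two statements limit what can be read from this. F2 opens with "Following is a summary of study procedures", and it later contains a note that begins "Please note that the protocol attached to Section S". That attached protocol is not among the documents available here.

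**The concern.** In a within-subject comparison of two boots, the second test can differ from the first for reasons unrelated to the boot, such as fatigue, warming up, or refitting of the pressure insole. These are examples; the documents mention none of them. If every subject has the same order, such an effect enters the device comparison in full.

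The plan gives no margin for comparability, so H1 will be read largely from the estimated difference, which is the quantity that an order effect shifts. The shift could go either way. It could make two unlike boots look comparable, or two like boots look different. Section G1 also says that the results will be used to size a larger superiority trial, so a shifted estimate could carry forward.

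**Working it through.** **Inputs.** The order and the walking distance come from F2. The within-subject design and the ANOVA come from G2. The sample size is 15 in Section D and F1 but 50 in G1, so both are used. The documents give no SD, significance level, margin or order effect, so there is no figure of the plan's own to reproduce. Two quantities below are assumptions: a two-sided 95% paired-t interval, and an order effect of *d* SDs of the paired difference.

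**Step 1: is the device effect identifiable?** Take a model with subject, device and test position (first or second). Under the fixed order the device and position columns are identical.

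| Design | Parameters | Rank, fixed order | Rank, counterbalanced |
|---|---|---|---|
| N=15, one visit | 15 + 2 = 17 | 16 | 17 |
| N=50, one visit | 50 + 2 = 52 | 51 | 52 |
| N=15, two visits (one visit term added) | 18 | 17 | 18 |
| N=50, two visits (one visit term added) | 53 | 52 | 53 |

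The fixed order is one rank short in every case. This result needs no assumed number. The expected estimate is the device effect plus *d*, at any N.

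**Step 2: what would an order effect do?** With the SD of the paired difference set to 1:

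- SE = 1/√N, which is 0.258 at N=15 and 0.141 at N=50.
- 95% half-width = t(0.975, N−1) × SE, which is 2.145 × 0.2582 = 0.554 at N=15 and 2.010 × 0.1414 = 0.284 at N=50.
- Coverage of the true device difference = 1 − the two-sided tail of a noncentral t with N−1 degrees of freedom and noncentrality *d*√N. For *d* = 0.1 the noncentrality is 0.387 at N=15 and 0.707 at N=50.

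| Assumed *d* | Coverage, N=15 | Coverage, N=50 |
|---|---|---|
| 0.05 | 94.6% | 93.6% |
| 0.1 | 93.5% | 89.3% |
| 0.2 | 88.8% | 71.6% |

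Coverage falls faster at N=50 because the interval narrows while the shift stays the same.

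**Step 3: what does counterbalancing do?** The device effect is the average of the two order-specific mean differences, with N−2 degrees of freedom.

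- SE = 0.5 × √(1/n₁ + 1/n₂). For 8/7 this is 0.5 × √(1/8 + 1/7) = 0.259. For 25/25 it is 0.141.
- Half-width: 2.160 × 0.2588 = 0.559 at N=15, and 2.011 × 0.1414 = 0.284 at N=50.
- In 100,000 simulated trials per case with *d* = 0.2 and 0.5 and no true device difference, the mean bias was at most 0.002 SD. Rejection at a nominal 5% was 4.9% to 5.1%.

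This assumes an additive order effect without differential carryover.

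**The case against.** The evidence for a fixed order is two words in a section that calls itself a summary. The sentence may only be naming two conditions. The neighbouring gait paragraph describes the devices the other way round (PulseFlow DF, then the removable cast walker), which suggests loose drafting. The attached protocol might vary the order. This stands as a limit: it lowers confidence that a fixed order is intended, but the text as written still states a sequence and nothing offsets it.

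A material order effect may be unlikely. The walk is about 20 feet. If the tests run as listed, each subject has already walked 20 m at two speeds in both devices, or 4 × 20 = 80 m, during the gait test. That would plausibly reduce first-use and warm-up effects. It bears on severity but leaves the aliasing in place.

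F2 gives comparability as the purpose of the standing test and introduces the whole assessment as one of pressure reduction, so the link from walking data to H1 could be questioned. It narrows but survives: G2 frames H1 around in-shoe pressures in general and includes pressure-time integrals, so walking data plausibly feed it. Walking pressure also falls under the primary endpoint in Section D.

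Finally, this is a proof-of-concept pilot with no margin or confirmatory rule for plantar pressure. That is a fair reason to keep the grading modest.

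A reader might infer that the comparison is biased in favour of PulseFlow DF, or that the plantar-pressure endpoint is invalid. The documents do not support either, because they show neither that an order effect exists nor its direction. Nor do they show a fixed order for the standing test, and gait is a separate outcome.

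**Conclusion.** The point holds for the walking test, on the text available. If the stated sequence is followed, device and test position are fully aliased, and neither a larger sample, the Visit 4 repeat nor later modelling can separate them. Confidence in that is high. Confidence that a fixed order is actually intended is moderate.

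The practical size is unknown. The coverage figures illustrate what assumed effects would do and are not estimates for this trial; the 71.6% in particular pairs the largest assumed effect with the larger of the two sample sizes. Severity is low to moderate. The case for change is that the remedy is almost free and cannot be applied once the data are in.

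**What to change.** First check the protocol attached to Section S. If the order is already varied there, one sentence in F2 settles the matter. If not:

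- **F2, walking test.** Replace the stated sequence with wording such as: *in both the standard offloading boot and PulseFlow DF; the boot tested first is assigned from a pre-printed 1:1 blocked random list, and the order is recorded.*
- **G2, H1.** Add test order to the ANOVA for walking pressure. Define the device effect as the average of the two order-specific mean differences. State the assumption of an additive order effect without differential carryover. The Fisher's exact tests need no change for this point.

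**Cost.** A list to administer and one degree of freedom, with no extra walks, visits or patients. The 95% half-width goes from 0.554 to 0.559 SD at N=15 and stays at 0.284 SD at N=50. If missing data left a 10/5 split at N=15, the SE would be 0.5 × √(1/10 + 1/5) = 0.274 SD instead of 0.259.

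**Limit.** By Visit 4 subjects will have used PulseFlow DF for four weeks. Counterbalancing does not remove that greater familiarity, and the text does not say which visit supplies H1.
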